Study Title: Locomotor Response of Persons with Upper Limb Loss to Treadmill Perturbations

NCT: NCT04274218

Document Date: April 2nd 2024

Background and Study Design

The role of the upper limbs in gait dynamics has received little attention historically, however surmounting evidence supports an important function of the arms in balance during locomotion and other dynamic tasks. Regaining balance after a perturbation is contingent on reactive mechanisms for re-stabilization. Rapid arm elevation is commonly observed in ablebodied individuals following a perturbation, which acts to increase the moment of inertia (I), slowing trunk motion. In any movement context, it is plausible that the result of a perturbation, i.e., a fall or recovery, could rest on the ability to effectively manipulate arm motion. A high fall rate has been observed in individuals with upper limb absence (ULA). A large proportion of falls in persons with ULA (67%) has been reported to occur during walking activities. Effects of ULA-induced imbalance can be observed in an increase in sound arm swing during walking. Use of an upper limb prosthesis, which effectively reduces the mass discrepancy, might be a solution to this issue of imbalance. Reactive responses are yet to be explored in individuals with ULA with and without use of a prosthesis. The objective of this cross-over intervention study was to investigate the reactive responses of people with ULA to perturbations during walking.

Protocol

Participants completed two baseline walking trials and 12 perturbation trials on an instrumented treadmill (Motek, Enschede, Netherlands). Baseline trials consisted of 30 seconds of steady-state walking, first at a self-selected speed then 1.0 m/s. The perturbation was designed to disrupt walking and instigate trip-like responses: the treadmill belt was programmed to accelerate (6.5 m/s^2) to 3.3 m/s, then immediately decelerate (6.5 m/s^2) to 1.0 m/s. During each trial a perturbation was triggered at initial contact of a randomly-selected step between 21 and 40 after

the belt reached 1.0 m/s and delivered during single limb stance of the sound/dominant or impaired/non-dominant arm side (6 per side). Participants walked for twenty strides after restoration of reciprocal gait before the treadmill was stopped. Side/step randomization minimized anticipatory effects of knowledge of the perturbation timing on motor response. Prosthesis users completed all tasks with and without their customary prosthesis, order randomized.

Mass, COM location and *I* of each prosthesis were estimated using an oscillation cage and reaction board. *I* was estimated about the medial-lateral axis of rotation at the prosthesis proximal end and translated to its COM using the parallel axis theorem.

Data Analysis

Kinematic data were collected with a 12-camera motion capture system (Motion Analysis, Rohnert Park, CA) at 120 Hz. Data were exported to Visual 3D (C-motion, Germantown, MD), filtered using a 4th-order low-pass (9 Hz) Butterworth filter, and a customized 12-segment model was applied. The assumption of uniform density [36] was applied to estimate segment mass as a percentage of body mass, COM position and *I*, except for the ULA impaired limb where the forearm was modified based on the prosthesis condition.

Initial contact events were labelled using a velocity-based algorithm and corrected manually. *L* was estimated by calculating the instantaneous angular momentum of each segment about the COM in three planes, summing the values according to Eq. 1, where, for each segment i, $\vec{w_i}$ is the angular velocity, $\vec{r_i}$ is the distance from segment COM to whole-body COM, m_i is the mass and $\vec{v_i}$ is relative velocity.

$$\vec{L} = \sum_{i=1}^{n} \vec{I}_{i} \vec{\omega}_{i} + \vec{r}_{i} \times m_{i} \vec{v}_{i}$$
 Eq. 1

L was normalized by treadmill speed and participant mass and height. L_{range} was calculated as maximum minus minimum *L* over the period of interest. For baseline trials, L_{range} was calculated over each stride and averaged over the middle 10 strides. The perturbation recovery phase was defined as perturbation onset time to the seventh initial contact, and L_{range} was calculated from global maximum and minimum across that period. To aid interpretation of L_{range} , bilateral shoulder flexion-extension and add-abduction ranges were calculated similarly for each period of interest. Shoulder flexion-extension was defined as the sagittal-plane angle between the upper arm long axis (line connecting shoulder and elbow markers) and thorax long axis (line connecting midpoint between shoulder markers and pelvis center) and add-abduction angle was that relative angle in the coronal-plane. Five perturbation trials on each side were averaged with the first (naïve) trial excluded because of exaggerated reactions to first-side perturbation.

Statistical Analysis

Descriptive statistics are produced for L_{range} (recovery minus baseline), shoulder joint range-of-motion during recovery, maximum trunk flexion angle, and maximum trunk flexion velocity for each condition (controls: with arms free and with non-dominant arm bound; upper limb absence: without wearing the prosthesis and with wearing the prosthesis).

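### Condition order is randomised but results are summarised by condition only, so any change in response between the first and second block can enter the prosthesis comparison by chance and adds spread

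*Combined protocol and SAP*

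**What the plan says.** The Background and Study Design section describes a cross-over: "The objective of this cross-over intervention study was to investigate the reactive responses of people with ULA to perturbations during walking". The Protocol section sets the tasks ("Participants completed two baseline walking trials and 12 perturbation trials on an instrumented treadmill"), with perturbations "delivered during single limb stance of the sound/dominant or impaired/non-dominant arm side (6 per side"), and adds: "Prosthesis users completed all tasks with and without their customary prosthesis, order randomized". On the natural reading, a prosthesis user completes 12 perturbation trials in one condition and 12 in the other.

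On exposure, the Data Analysis section states: "Five perturbation trials on each side were averaged with the first (naïve) trial excluded because of exaggerated reactions to first-side perturbation". The Protocol section also notes: "Side/step randomization minimized anticipatory effects of knowledge of the perturbation timing on motor response". That concerns anticipation of when a perturbation will come, not a change in response over repeated blocks.

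The Statistical Analysis section plans descriptive statistics for each condition. For participants with limb absence the conditions are "upper limb absence: without wearing the prosthesis and with wearing the prosthesis"; for controls they are arms free and non-dominant arm bound. No order, sequence or block summary is named. The documents do not give the number of participants, how order was generated, how many had each order, the interval between conditions, or any order for the controls' conditions.

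**The concern.** In a two-period cross-over, order is part of the design, and an analysis that ignores it gives up the means of separating a period effect from the condition effect. Here the plan itself observes that a first exposure provokes a larger reaction. By the second condition a participant has, on the natural reading, already met 12 perturbations. If responses still differ between blocks after the naïve trial is removed, the two condition summaries differ partly because of who did what first. Taking each person's with-minus-without difference does not remove this, because the block effect carries opposite signs in the two orders.

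The stake is interpretive. The background presents the prosthesis as a possible remedy for imbalance, so readers will compare the with and without summaries, and a descriptive plan has no later model in which order could be adjusted for.

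**Working it through.** **Inputs from the documents.** 12 perturbation trials, 6 per side, five per side averaged. Check: 12/2 − 1 = 5, which agrees. There is no sample-size or power figure to reproduce.

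**Assumed inputs.** N = 6, 10 or 20; order set by simple coin-flip; block effect π (second block minus first) of 0.25, 0.5 or 1.0, in units of the SD of the within-person difference.

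**Step 1: the simple mean difference.** Let τ be the prosthesis effect. The expected with-minus-without difference is τ − π for those who wore the prosthesis first and τ + π for those who went without first. Hence

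mean difference = τ + π × (n_without-first − n_with-first)/N.

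Under randomised order the second term has expectation zero. It is exactly zero with equal orders.

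**Step 2: how large the imbalance could be.** With B ~ Binomial(N, 0.5), the share of π entering is |2B − N|/N:

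| N | mean share | chance of exact balance | chance that at least half of π enters |
|---|---|---|---|
| 6 | 0.31 | 31% | 22% |
| 10 | 0.25 | 25% | 11% |
| 20 | 0.18 | 18% | 4% |

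At N = 10 the chance of 7:3 or worse is 2 × (120 + 45 + 10 + 1)/1024 = 352/1024 = 34%. A 7:3 split puts 0.4π into the simple difference: 0.10, 0.20 or 0.40 SD for the three values of π.

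**Step 3: spread.** With f the imbalance fraction, the SD of the within-person differences is multiplied by √(1 + π²(1 − f²)). With equal orders (f = 0) this is 1.03, 1.12 or 1.41. For a by-condition SD, which is nearer to what the plan reports, the added variance is π²/4. With π now in units of that SD, the factor is √1.0625 = 1.03 at 0.5 and √1.25 = 1.12 at 1.0.

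**Step 4: the adjusted estimate.** The average of the two order-specific means is [(τ − π) + (τ + π)]/2 = τ at any split with both orders present. Half their difference estimates π.

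**Step 5: its price.** At the same within-order variance, its SE relative to the simple mean is √(N²/(4·n1·n2)): √(100/84) = 1.09 at 7:3 and √(36/20) = 1.34 at 5:1. At N = 10 split 7:3, its variance is ¼(1/7 + 1/3) = 0.119, against 0.100 for the simple mean, whose squared bias is 0.16π². The adjusted estimate therefore has the smaller mean squared error only when π exceeds √(0.019/0.16), about 0.35 SD. That is a reason to show both.

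**The case against.** The strongest reply is that randomised order already does the main job. A reader might infer that habituation biases the prosthesis result; the documents do not support that. The expected bias is zero, and silence about balancing does not show that orders were unequal.

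A reader might also infer that the plan documents a continuing decline in response. It does not. The only exaggeration reported is on the naïve trial, and that trial is excluded: an excess E in one of six trials would have shifted that side's mean by E/6, and shifts it by nothing once dropped. A decline over later trials, or from one block to the next, is inference, and π could be near zero.

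Three further points stand. The plan defines no with-minus-without estimator, so the effect is on how readers compare two summaries. No beneficial direction is declared: the background describes arm elevation as slowing trunk motion, so a smaller shoulder range cannot simply be read as improvement. And the adjusted estimate costs precision when orders are unequal, needs both orders represented (at N = 6 under coin-flip order, 2/64 = 3% of samples would have only one), and assumes no differential carry-over.

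These points limit the claim without removing it. Zero expected bias does not protect one small realised sample, and the extra spread remains at equal orders. It is also unclear whether the naïve-trial rule applied in both blocks or only in the first; in a second block the participant is no longer naïve.

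**Conclusion.** The concern holds in a limited form. The plan randomises order and then leaves it out of its summaries, so any block effect can enter the with-versus-without comparison by chance and inflate the spread of within-person differences. It is worth correcting because the remedy needs only the recorded order. All magnitudes are illustrative: under coin-flip order the mean share of the block effect entering is 31%, 25% and 18% at N = 6, 10 and 20, and at equal orders the SD of within-person differences rises by 3%, 12% or 41% for block effects of 0.25, 0.5 or 1.0 SD. None of N, the block effect or the coin-flip assumption comes from the documents.

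For controls, a reader might infer a fixed order of arms free and arm bound, because the randomisation statement covers prosthesis users only. That is a gap in reporting, not evidence of a fixed order. If there was one, however, the whole block effect would sit in that comparison and no analysis could separate it.

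**What to change.** - State how order was generated and how many participants had each order.
- Summarise each outcome by order and block, where numbers allow.
- Report the within-person with-minus-without difference in two forms: the simple mean, and the average of the two order-specific means. Give the estimated block effect alongside.
- State the limits of the adjusted form: an SE about 9% larger at 7:3 (34% at 5:1), both orders required, and no differential carry-over assumed.
- State how the naïve-trial exclusion was applied in each block.
- For controls, use the recorded order in the same way. If all followed one order, say that the free-versus-bound difference cannot be separated from a block effect.

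The cost is one variable, one degree of freedom and a few lines of analysis. No new data are needed, provided order was recorded.

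### Does normalising angular momentum by treadmill speed leave the change in L_range resting on inconsistent divisors?

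*Combined protocol and SAP*

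**What the plan says.** Three parts of the combined protocol and SAP bear on this.

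- **Protocol, baseline.** "Baseline trials consisted of 30 seconds of steady-state walking, first at a self-selected speed then 1.0 m/s". No value is given for the self-selected speed.
- **Protocol, perturbation.** In each perturbation trial the trigger step is counted from when "the belt reached 1.0 m/s". The pulse itself is described thus: "the treadmill belt was programmed to accelerate (6.5 m/s^2) to 3.3 m/s, then immediately decelerate (6.5 m/s^2) to 1.0 m/s".
- **Data Analysis.** After Eq. 1 defines whole-body angular momentum L, the text states "L was normalized by treadmill speed and participant mass and height". L_range is then the spread between the largest and smallest L in the period of interest. For steady walking: "For baseline trials, L_{range} was calculated over each stride and averaged over the middle 10 strides". For recovery: "The perturbation recovery phase was defined as perturbation onset time to the seventh initial contact". Within that window a single range is taken, between the overall highest and lowest values.

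The Statistical Analysis section lists descriptive statistics for the recovery value of L_range less its baseline value, together with shoulder range of motion and two trunk measures. It does not name the baseline trial that is subtracted. It specifies no hypothesis test and designates no primary outcome.

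**The concern.** A divisor called treadmill speed is unambiguous only while the belt runs steadily. The recovery window opens at perturbation onset, so the whole belt pulse falls at its start. Eq. 1 gives L at each instant, and the normalisation is described before the range is taken. A reader could therefore divide each instant of L by the belt speed at that instant. That would shrink L by up to 3.3 times while the trip response is being provoked, and the result would depend on whether the L peak falls during or after the pulse, a matter of timing rather than size of response. If timing differed between arm conditions, the distortion would not cancel in the comparison.

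The second worry is the subtracted baseline. There are two baseline trials, and only one shares the speed of the perturbation trials. If the self-selected trial were used, recovery and baseline would come from different walking speeds and carry different divisors, and a person's preferred pace could appear as part of the reactive response.

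**Working it through.** The documents give no figure for the normalised outcome, so there is nothing to reproduce. The check is what each reading of the divisor would do.

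**Inputs from the Protocol section:** belt 1.0 m/s before and after the pulse, peak 3.3 m/s, both ramps at 6.5 m/s².

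**Assumed, because the documents are silent:** step time 0.4 to 0.7 s; recovery window of 6 or 7 steps; self-selected speed 0.8 to 1.4 m/s; raw recovery range R = 2 times the raw baseline range, with the latter set to 1.

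**Step 1, the pulse.** One ramp lasts (3.3 − 1.0)/6.5 = 0.354 s. The pulse lasts 2 × 0.354 = 0.708 s, with mean belt speed (1.0 + 3.3)/2 = 2.15 m/s. The window T is between 6 × 0.4 = 2.4 s and 7 × 0.7 = 4.9 s, so the pulse fills 0.708/4.9 = 14% to 0.708/2.4 = 29% of it.

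**Step 2, recovery divisor, with the 1.0 m/s baseline.** Change score = R/d − 1/1.0.

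| Reading of treadmill speed | d (m/s) | Effect on normalised recovery range | Change score, R = 2 |
|---|---|---|---|
| Set trial speed | 1.0 | none | 2/1.0 − 1 = +1.00 |
| Mean over the window | 1.17 to 1.34 | 14% to 25% lower | 2/1.17 − 1 = +0.71 (+0.72 unrounded) to 2/1.34 − 1 = +0.49 |
| Peak | 3.3 | 70% lower | 2/3.3 − 1 = −0.39 |

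The window mean is [1.0 × (T − 0.708) + 2.15 × 0.708]/T, evaluated at T = 4.9 and T = 2.4.

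**Step 3, instant-by-instant divisor.** Belt speed is 1.0 + 6.5 × 0.2 = 2.3 m/s at 0.2 s, about 2.35 m/s at 0.5 s, and 1.0 m/s from 0.708 s on. The effect on L_range then depends on the waveform, which the documents do not give. In invented traces (Gaussian peak, SD 0.15 s, 1.5 to 4 times baseline, at 0.2 to 0.5 s), the range fell to between about 32% and 76% of its constant-divisor value, depending on the other features assumed. With the peak at 0.7 s or later, traces with a baseline oscillation kept 97% to 100%. These figures describe the assumed traces, not the trial.

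**Step 4, self-selected baseline divided by its own speed s.** With raw L held fixed, the normalised baseline is 1/s, that is 1/0.8 = 1.25 to 1/1.4 = 0.71, and the change score runs from 2 − 1.25 = +0.75 to 2 − 0.71 = +1.29. If raw L were instead proportional to speed, the normalised baseline would be s/s = 1 and the score +1.00 at any s. The +25% and −29% are divisor ratios, not estimates of bias.

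**Step 5, which reading the text supports.** Speed stands in one list with body mass and height, both constants for a person. The units agree with a constant: L is in kg·m²/s, and mass × height × speed is also in kg·m²/s, so the step yields a dimensionless quantity. Where the text speaks of an instantaneous quantity, it refers to segment angular momentum; no time-varying, mean or peak belt speed is mentioned. Perturbation trials are set at 1.0 m/s, and a baseline was recorded at that same speed. With d = 1.0 in both terms, the change score is R − 1.

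**The case for a change.** The strongest case for acting is that the ordinary reading is inferred, not written. On that reading the speed step divides by 1.0 in every window entering the change score, so it alters no value there, and a reader may fairly ask whether something else was done. Baseline trials are mentioned in the plural, and neither is named as the reference. A divisor common to everyone would still alter the weight of recovery against baseline in a difference. Planning only descriptive statistics does not excuse an undefined quantity, and one sentence would settle it.

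What stands is that two definitions are unwritten. The rest is weaker. The step is not idle on the ordinary reading: it makes the measure dimensionless and puts the self-selected trial on its own speed scale. The sign reversal needs the peak speed as divisor, which nothing in the text suggests. The programmed belt profile is described once, with no variation by group or arm condition, so any fixed recovery divisor rescales everyone's recovery value alike. Nor is the remedy of dividing every window by 1.0 m/s harmless: taken at its word, it would divide the self-selected trial by a speed at which it was not walked.

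**Conclusion.** No change to the plan follows. The Data Analysis section leaves the divisor and the subtracted baseline unstated, but the Protocol section supplies one coherent pair: a set speed of 1.0 m/s in the perturbation trials and a baseline recorded at 1.0 m/s. With that pair the divisors are identical and the normalisation introduces no distortion. An analyst choosing a comparator for trials run at 1.0 m/s has every reason to take the matching trial and to keep the self-selected trial as a separate description at its own speed.

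The alternative readings are not trivial in size: 14% to 25% off the recovery range with a window mean, 70% with the peak, and a waveform-dependent loss with an instant-by-instant divisor. They rest on divisors that the text does not mention and, apart from the 70%, on assumed step times or traces. The self-selected baseline figures also assume that raw L does not change with speed. The conclusion itself rests on reading speed as a constant, like mass and height. It would be overturned only by evidence that a varying divisor or the self-selected baseline was actually used, and the documents contain none.

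### The cross-over is summarised one condition at a time, so the spread and precision of each person's with-minus-without-prosthesis change are not reported

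*Combined protocol and SAP*

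**What the plan says.** Background and Study Design presents a cross-over: "The objective of this cross-over intervention study was to investigate the reactive responses of people with ULA to perturbations during walking". The gap in knowledge it names is the comparison of the two prosthesis states: "Reactive responses are yet to be explored in individuals with ULA with and without use of a prosthesis". The Protocol section creates the pairing: "Prosthesis users completed all tasks with and without their customary prosthesis, order randomized".

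The Statistical Analysis section is a single sentence: "Descriptive statistics are produced for L_{range} (recovery minus baseline), shoulder joint range-of-motion during recovery, maximum trunk flexion angle, and maximum trunk flexion velocity". The unit of summary is fixed at its end, "maximum trunk flexion velocity for each condition", and the conditions are then listed. For limb absence they are "upper limb absence: without wearing the prosthesis and with wearing the prosthesis"; for the comparison group, "controls: with arms free and with non-dominant arm bound".

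The only change score in that sentence is recovery minus baseline for the angular-momentum range. It is taken inside one condition and does not compare prosthesis states. No with-minus-without difference, paired SD, interval or paired model appears anywhere. The documents do not say whether each control was tested in both arm conditions.

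**The concern.** In a cross-over each person serves as his or her own control. The gain depends on how closely a person's two results agree, and it shows only when the two results are subtracted person by person. A table with one column per condition keeps the mean contrast but discards the link between the two values.

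A reader of such a table could not attach a standard error to the prosthesis contrast. Nor could the reader tell a change seen in nearly every participant from a mixture of rises and falls with the same average. For a study that raises the prosthesis as a possible remedy for imbalance, that leaves the central comparison without any measure of uncertainty or consistency.

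**Working it through.** **Inputs.** The documents state no sample size, SD, within-person correlation or expected change, so there is no planned figure to reproduce. Everything below is assumed and shown over a range: correlation rho from 0 to 0.9; n = 6, 10 or 20 pairs; the same SD in both conditions, used as the unit; and, for the last column only, a mean change of 0.5 SD with normally distributed differences.

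**Formulas.**

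- SD of the paired difference: SD_diff = sqrt(s1² + s2² − 2·rho·s1·s2). With s1 = s2 = SD this is SD × sqrt(2(1 − rho)).
- 95% half-width for the mean difference: t(0.975, n − 1) × SD_diff / sqrt(n), with t = 2.571, 2.262 and 2.093 at n = 6, 10 and 20.
- Share of observed changes opposite in sign to the mean: Φ(−0.5 / sqrt(2(1 − rho))).

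| rho | SD_diff | Half-width, n = 6 | n = 10 | n = 20 | Opposite direction |
|---|---|---|---|---|---|
| 0 | 1.414 | 1.484 | 1.012 | 0.662 | 36% |
| 0.3 | 1.183 | 1.242 | 0.846 | 0.554 | 34% |
| 0.5 | 1.000 | 1.049 | 0.715 | 0.468 | 31% |
| 0.7 | 0.775 | 0.813 | 0.554 | 0.363 | 26% |
| 0.9 | 0.447 | 0.469 | 0.320 | 0.209 | 13% |

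The cell means and SDs are the same in every row. From top to bottom the SD and the interval width shrink by 1.414 / 0.447 = 3.2 times.

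**What the cells alone allow.** They bound SD_diff only between |s1 − s2| and s1 + s2, which is 0 to 2 SD when the SDs are equal.

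**Check with made-up data, without assuming rho.** Let six people score 1, 2, 3, 4, 5, 6 without the prosthesis, and let the values with it be 2 to 7 in some order. The cells are always mean 3.5 and 4.5, SD 1.87 each, and the mean change is 1.0.

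| Values with prosthesis, in person order | Changes | SD of change | 95% CI for mean change |
|---|---|---|---|
| 2, 3, 4, 5, 6, 7 | 1, 1, 1, 1, 1, 1 | 0.00 | 1.0 to 1.0 |
| 4, 2, 6, 3, 7, 5 | 3, 0, 3, −1, 2, −1 | 1.90 | −0.99 to 2.99 |
| 7, 6, 5, 4, 3, 2 | 6, 4, 2, 0, −2, −4 | 3.74 | −2.93 to 4.93 |

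The planned table would be identical for all three data sets.

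**The case against.** **The plan does not rule out a paired summary.** It names no particular statistics, and listing individual values or drawing linked plots would keep the pairing. That is fair as to what might be reported. But the sentence fixes the unit of summary and lists the conditions, so following it as written yields no paired result. The loss described here is from cell summaries; the individual data still hold the information.

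**The aim is broad and descriptive, with no test declared.** True, but the mean and SD of a difference are themselves descriptive statistics. No test is being asked for.

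**None of the numbers comes from this trial.** Correct. They illustrate a general identity and do not measure a loss in these data. The upper bound of 2 SD needs a correlation of −1, which is extreme for repeated measures on one person. The conclusion that cells do not determine the paired spread needs none of these values.

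**The spread of observed changes is not the spread of true responses.** With one comparison per person it also contains within-person noise and any period or order effect. This stands: the opposite-direction percentages concern observed changes only. Adaptation is plausible, because the Data Analysis section drops the first trial on account of exaggerated reactions. With unequal numbers in the two orders, a period effect would shift the difference in cell means and the pooled paired mean alike. That supports adding a summary by order; it does not support leaving the paired summary out.

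**Cell membership may matter more.** Two-condition testing is described for prosthesis users, while the cells are labelled for limb absence generally. The documents do not show that non-users were enrolled. If any sit only in the without-prosthesis cell, even the difference in cell means is not a within-person change. This strengthens the case for the fix.

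**Conclusion.** The concern holds. As written, the plan gives no measure of the spread or precision of the with-minus-without change, which is the contrast the cross-over was built to estimate. The mean change is unaffected provided both cells hold the same people. Under the stated assumptions the missing SD could differ about threefold between correlations of 0 and 0.9, with identical published cells. At an assumed 10 pairs, that separates a half-width of 1.01 SD from one of 0.32 SD. The sizes are illustrative, but the non-recoverability from cell means and SDs is exact. No reported result is wrong for this reason. It is a change that should be made, not a flaw that invalidates the study.

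**What to change.** For each of the four outcomes, among limb-absence participants who completed both conditions, report the without-prosthesis value, the with-prosthesis value, and the mean and SD (or 95% confidence interval) of the with-minus-without difference. Give n for every cell. If controls did both arm conditions, report the same paired difference for them. If anyone completed only one condition, show those people in a separate row so that the comparison stays within person. A breakdown of the paired difference by testing order would be a useful addition.

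The cost is small. The data are already collected and no new measurement is needed. The work is one derived difference per analysed variable. That is somewhat more than four columns, because angular momentum is computed in three planes, shoulder range is bilateral in two directions, and trials are averaged by side. Since the documents report conduct in the past tense, label the paired summary as added after data collection if that is the case.
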